1.4.2.3 Other assessments

Haematology collected at V1 as baseline characteristics.

1.4.2.4 Withdrawal/discontinuation

In accordance with the Declaration of Helsinki (in accordance with the applicable country's acceptance), each subject is free to withdraw from the study at any time. The investigator also has the right to withdraw a subject from the study in the event of concurrent illness, AEs, pregnancy, or other reasons concerning the health or wellbeing of the subject, or in the case of lack of cooperation. In addition, a subject may be withdrawn from the study as described in Sections 3.6, 5.2.4.2, 6.2 and 8.1.7 of the protocol.

Should a subject decide to withdraw from the study after administration of IMP, or should the investigator decide to withdraw the subject, all efforts will be made to complete and report the observations up to the time of withdrawal as thoroughly as possible. A complete final evaluation at the time of the subject's withdrawal should be made and an explanation given of why the subject is withdrawing or being withdrawn from the study.

The reason for and date of withdrawal from the study must be recorded on the eCRF. If a subject withdraws consent, every attempt will be made to determine the reason. If the reason for withdrawal is an AE or a clinically significant laboratory test abnormality, monitoring will continue until the event has resolved or stabilised, until the subject is referred to the care of a local health care professional, or until a determination of a cause unrelated to the IMP or study procedure is made. The specific AE or test result(s) must be recorded on the eCRF. All evaluations should be performed, according to the protocol, on the last day the subject receives IMP, or as soon as possible thereafter. If the final visit is conducted more than 47 days after the dose of IMP, all safety evaluations will be performed. It is not planned to collect efficacy data after V2.

20/62

1.4.3 Schedule of assessments

		iy i roccuures un		
Study Period	Baseline/ Treatment	Colonoscopy	Phone contact	End of Study (or in case of Early Withdrawal*)
Visit	1	2	3	4
Dav	Dav 1	Day 2	Day 4	Day 32
Window			±1	-5/+15 i.e. Day 27 to Day 47
Eligibility Criteria	X			
Demographic Data	X			
Blood Pregnancy Test [a]	X			
Informed Consent (parent(s)	X			
or legal representative)				
Assent (subject)	X			
Medical and Surgical History	X			
Indication(s) for Colonoscopy	X			
Prior and Concomitant	X	X		X
Medication [b]	21	21		11
Prior and Concomitant Non-	X	X		X
Drug Therapy [b]	21	21		21
AFs [c]	X[d]	X	X[e]	X
Physical Examination	X[u]			X
Vital Signs (Temperature	X	X		
blood pressure (BP) and heart	Λ	1		X
rate (HR))				
Body Weight and height[f]	X	X		X
Blood sample collection [g]		X YG		
[b]	Λ [1]	ΛIJJ		A
Urine sample collection[k]	X	X		X
Blood and urine sulfates[1]	X	X[i]		
BANDOMISATION [m]	X X			A
Study treatment dispensation	X			
(with explanation of treatment	Λ			
administration)				
Subject/caregiver leaflet	x			
dispensation by study nurse	21			
(with explanation of				
questionnaires including				
compliance measurement)				
Subject takes treatment	Х			
preparation				
Completion of leaflet				
questionnaires by subject/				
caregiver/ nurse				
• Treatment /	Х			
Compliance				
	V			
• I reatment	Λ			
Acceptability				
Symptom Scale	Х			
(Tolerability)				
Collection of leaflet		x		
questionnaires by study nurse		Δ		
Drug accountability/ study		x	 	
administration compliance by				

Table 5 Study Procedures and Assessments

Study Period	Baseline/ Treatment	Colonoscopy	Phone contact	End of Study (or in case of Early Withdrawal*)
unblinded site member				
Colonoscopy assessment [n]		Х		
Subject status at the end of the visit	Х	Х	Х	Х

*Early withdrawal will be anytime from Visit 1

- [a] If applicable. Urine pregnancy test will be performed only when blood tests including pregnancy have been performed prior to Visit 1.
- [b] Prior and concomitant medication and non-drug therapy will from 7 days before baseline and for any action taken by the investigator
- [c] AEs will be actively collected by the investigator and subjects will be instructed to contact the investigator if they experience any AEs
- [d] At baseline, AEs will be collected from the date of informed consent and assent signature
- [e] The investigator will contact the subject by phone on Day 4±1 to collect data on potential AEs
- [f] Height will be measured at Baseline only
- [g] Local laboratory (blood): biochemistry including: anion gap, alanine aminotransferase (ALT), aspartate aminotransferase (AST), creatine phosphokinase (CPK), lactic dehydrogenase (LDH), gamma-glutamyl transferase (GGT), total and conjugated bilirubin, creatinine, urea, serum electrolytes (sodium, potassium, chloride, calcium, magnesium, phosphate, bicarbonate), alkaline phosphatase, albumin, total protein, C reactive protein (CRP), uric acid, creatinine clearance (calculated GFR), osmolality
- [h] Laboratory assessments performed within 10 days or less prior to inclusion may be used to determine eligibility upon investigator agreement.
- [i] Additional local laboratory haematology: complete blood count (CBC), international normalised ratio (INR)
- [j] Blood sampling during anaesthesia
- [k] Local laboratory urine analysis (by dipstick), microscopic examination
- [1] Collection of blood and urine sample for central laboratory sulfate dosage
- [m] Randomisation if satisfactory biochemistry results
- [n] Colonoscopy assessment: Rescue treatment, cleansing Score, BBPS, start time of colonoscopy, time of caecal intubation, caecum reached, withdrawal time, diagnosis/findings.

	During/after Dose 1	During/after Dose 2
	Day 1	Day 1
Treatment/Compliance Questionnaire[a]	Х	Х
Treatment Acceptability Questionnaire	Х	Х
Symptom Scale (Tolerability)	Х	Х
Information about time to bowel movement		Х
and time to first clear watery stool.		

Table 6 Su	ibject's	Leaflet	Collected	Information
------------	----------	---------	-----------	-------------

[a] Treatment/Compliance questionnaire will collect information about: preparation of treatment, treatment intakes (recording of residual volumes, start/end times) for Eziclen®/Izinova® or Klean-Prep®.

1.4.4 Planned sample size

The primary aim of the study is to show that Eziclen®/Izinova® is non-inferior to Klean-Prep® in the proportion of subjects with successful colon cleansing.

A non-inferiority margin of 15 % has been selected for consistency with other studies in colon cleansing preparations.

Therefore assuming a success rate (excellent or good response) of 85 % in both the Eziclen®/Izinova® and Klean-Prep® groups, a one-sided alpha of 0.025 and 90 % power, 120 subjects are required per treatment group. Assuming a rate dropout/non-compliance to protocol of 4 % based on previous studies and taking into account that subjects will be hospitalised for treatment administration, 125 subjects will be randomised in each treatment

22/62

group, i.e. 250 subjects in total. Enrolment will be completed once 250 subjects have been randomised.

The primary endpoint of treatment success will be tested sequentially (hierarchical structure) with the first test being non-inferiority test based upon the treatment difference. A rejection of the null hypothesis will trigger superiority testing based upon the treatment difference.

The two hypothesis tests are hierarchically structured so that the second test (superiority) will only be considered if the first test (non-inferiority) is rejected. The superiority test is powered to detect an absolute difference of 18 %. There is no alpha adjustment for the second test as a result of the hierarchical testing.

2 SUBJECT POPULATIONS (ANALYSIS SETS)

2.1 Efficacy

2.1.1 Intention-To-Treat population (ITT)

The ITT population is:

All randomised subjects who received even a partial dose of study drug.

Subjects will be assessed according to their randomised treatment, regardless of the treatment they receive.

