- Urine analysis by dipstick (pH, protein, ketones, bilirubin, blood, urobilinogen, nitrites, leukocytes, glucose and specific gravity, urine microscopic examination
- Blood and urinary samples for sulphate measurement
- Blood pregnancy test, if female of child-bearing potential. Urine pregnancy test will be performed only when blood tests including pregnancy have been performed prior to Visit 1.
- Indication(s) for colonoscopy to be collected
- Randomisation
- Drug accountability, study treatment dispensation by study nurse (with explanation of treatment administration)
- Subject/caregiver questionnaires dispensation by study nurse (with explanation of questionnaires including compliance measurement)
- Prior and concomitant medications including supplements, herbal medications and nonprescribed compounds
- Prior and concomitant non-drug therapies and surgical procedures
- Collection of AEs from the time of informed consent signature
- Subject status at the end of the visit

Records up to the time of premature termination should be completed. In the event that the subject was not receiving IMP, the primary reason will be recorded.

If any Visit 1 serum chemistry result is considered abnormal and clinically significant by the investigator result may be checked per investigator's decision. The abnormal significant result will be reported as an AE.

In case of non-inclusion of the subject, the primary reason will be recorded.

Following confirmation of eligibility for the study, subjects will be given a randomisation/treatment allocation number and allocated to one of the dosing groups specified in Section 6.1.

Caregivers and subjects will be provided with a subject leaflet containing instructions on how to administer the study preparation. Caregivers will be provided with a Treatment Acceptability Questionnaire (see Section 7.3.2.3) to report their child's experience with the study preparation, and a Symptom Scale to rate subject tolerability (see Section 8.6). Subjects/caregivers will complete these questionnaires during and after the treatment administration.

Subjects will be hospitalised for preparation. The treatment will be prepared by a nurse and administration will be monitored as described in Section 3.4. The nurse or caregiver will fill in

PAGE 42/103

the questionnaires or ensure that the subject fills in, as appropriate. If a subject is unable to complete the preparation, a nasogastric tube will be placed.

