1.4 Methods and procedures

1.4.1 Subject identification and allocation to study treatment

All subjects enrolled will be identifiable throughout the study. The investigator will maintain a list of subject numbers and names to enable records to be found at a later date if required.

After eligibility is confirmed, at V1 (Baseline), subjects will be assigned to a randomisation number and to the associated treatment arm, in sequential order within each centre and within each country.

This will be provided by the electronic case report form (eCRF) which will assign the subjects to the first not-used randomisation number and so in a treatment arm according to the predefined randomisation list.

The investigator will under no circumstance change the randomisation number and the treatment arm allocated to the subject.

Recruitment will stop once 250 subjects have been randomised. Randomised subjects who terminate their study participation for any reason before starting the treatment will retain their randomisation number (the randomisation number will not be reused). The next subject is given the next randomisation number.

Randomised subjects who leave the study early will not be replaced.

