2.1.1 Modified Intention-To-Treat population (mITT)

The mITT population is:

All randomised subjects who received even a partial dose of study treatment and produced a primary efficacy assessment.

Subjects will be assessed according to their randomised treatment, regardless of the treatment they receive.

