2.1.2 Per Protocol population (PP)

The PP population is:

All subjects in the ITT population, who have undergone the colonoscopy procedure and for whom no major protocol violation/deviation impacting analyses (as defined in the Protocol Deviation Document) occurred.

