2.4 Other populations

2.4.1 Screened population

The screened population is:

All subjects screened (i.e. who signed the informed consent).

23/62

F-FR-58800-003

2.5 **Primary populations**

The primary analysis based on the primary efficacy endpoint will be performed on the mITT population. In that analysis, subjects who do not undergo colonoscopy because of inadequate preparation or preparation-related AEs will be considered as failures. In addition, robustness of primary efficacy results will be assessed by repeating the primary analysis on the PP population.

The analyses of safety data will be performed based on the safety population.

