3.2.1 Efficacy

The primary efficacy analysis will be performed on the mITT population as well as on the PP population to assess the robustness of the results. The secondary efficacy analyses will be performed on the ITT population and repeated on the mITT and PP if they differ from ITT from more than 10 %. The other efficacy analyses will be performed on the ITT population and repeated on the mITT from more than 10 %.

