3.2.1.3 Other efficacy analyses

Analysis of other efficacy endpoints will be performed on the ITT population.

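### Subjects who know their arm and decline it before the first dose enter no efficacy analysis; one all-randomised sensitivity analysis of the primary endpoint would show their effect

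*SAP*

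**What the plan says.** Three efficacy sets are defined, and each requires a dose.

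- ITT (SAP 2.1.1, Protocol 10.1): "All randomised subjects who received even a partial dose of study drug".
- mITT (also numbered SAP 2.1.1): "All randomised subjects who received even a partial dose of study treatment and produced a primary efficacy assessment".
- PP (SAP 2.1.2): "All subjects in the ITT population, who have undergone the colonoscopy procedure", with no major deviation that affects the analyses.

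The sets are used as follows. SAP 2.5: "The primary analysis based on the primary efficacy endpoint will be performed on the mITT population". SAP 3.2.1: "The secondary efficacy analyses will be performed on the ITT population". SAP 3.2.1.3: "Analysis of other efficacy endpoints will be performed on the ITT population". The robustness analyses in SAP 3.2.1.1 are a repeat on PP, an identity-link model on mITT and a bootstrap on mITT. The country and subgroup analyses of the primary endpoint are also on mITT.

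The plan foresees subjects who never start. SAP 1.4.1: "Randomised subjects who terminate their study participation for any reason before starting the treatment will retain their randomisation number". They are not replaced. Protocol 5.2.2 provides for the cause: "In the event that the subject was not receiving IMP, the primary reason will be recorded". SAP 3.2.4 tabulates, by arm and among everyone randomised, why subjects fall out of each analysis set.

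Protocol 3.4 and 3.8 keep the colonoscopist and investigator blind. Protocol 14.2.2 gives the subject either the Eziclen or the Klean-Prep leaflet once randomised.

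**The concern.** Leaving out randomised but undosed subjects does no harm when the decision not to start cannot depend on the arm. Here it can. The subject knows the product and sees the volume before intake: 2250 mL in total for Eziclen, against 70 mL/kg up to 4000 mL for Klean-Prep (SAP 3.2.1.2.10). The protocol itself links willingness to the preparation. Section 1.1 describes large-volume PEG solutions as often poorly tolerated, and Section 1.4 suggests that a lower volume may make patients more willing to undergo preparation.

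The rules that turn a missing evaluation into a failure (SAP 2.5, 3.2.1.1 and 3.2.3.1) do not reach these subjects. They operate within the mITT analysis, and a never-dosed subject is outside mITT.

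A refusal to start is arguably a failure of the preparation strategy. If refusals differ by arm, the dosed-only difference departs from the difference among all randomised subjects, and no planned analysis measures the gap.

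**Working it through.** **Inputs.** From SAP 1.4.4: success 85% in both arms, margin 15 points, one-sided alpha 0.025, power 90%, 120 evaluable and 125 randomised per arm, 4% dropout or non-compliance. The number of pre-dose refusers is not given. I assume 0 to 5 per arm, because 4% of 125 is 5.

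**The plan's own figure.** With unpooled variance, n = [0.85×0.15 + 0.85×0.15] × (1.960 + 1.282)² / 0.15² = 119.08, so 120 per arm. Then 120/0.96 = 125. Both figures reproduce, and power at 120 per arm is 90.2%.

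**Effect of one refuser.** Suppose d of 125 subjects are never dosed, dosed subjects succeed at 85%, and every dosed subject is assessed. The all-randomised rate is then 0.85 × (125 − d)/125. Each refuser costs 0.85/125 = 0.68 points. Five cost 3.4 points (85.0% to 81.6%), which is 3.4/15 = 23% of the margin.

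**Effect on the interval.** Lower limit = difference − 1.96 × √[p₁(1−p₁)/n₁ + p₂(1−p₂)/n₂], as an unadjusted Wald interval; the plan's own analysis adjusts for country. Successes are 85% of those dosed, rounded (102 of 120, 106 of 125). Differences are Eziclen minus Klean-Prep, in points.

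| Never dosed, Eziclen / Klean-Prep | Dosed only | All randomised |
|---|---|---|
| 5 / 0 | 102/120 v 106/125: +0.2, lower −8.8 | 102/125 v 106/125: −3.2, lower −12.5 |
| 0 / 5 | 106/125 v 102/120: −0.2, lower −9.2 | 106/125 v 102/125: +3.2, lower −6.1 |
| 5 / 5 | 102/120 v 102/120: 0.0, lower −9.0 | 102/125 v 102/125: 0.0, lower −9.6 |

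The one-sided cases move the difference by 3.4 points, in opposite directions. All six lower limits stay above −15.

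**Chance of clearing the margin.** Using the same normal formula with true rates of 85% among the dosed, the all-randomised analysis clears −15 with probability 69.2% at 5/0, 86.4% at 5/5 and 97.4% at 0/5. The dosed-only analysis stays between 90.2% and 91.3% in every case.

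**Near the margin.** Counts can be chosen for which the two analyses disagree.

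- Five Eziclen refusers: 96/120 v 106/125 has lower limit −14.3 (met), while 96/125 v 106/125 has −17.7 (not met).
- Five Klean-Prep refusers: 97/125 v 102/120 has −17.1 (not met), while 97/125 v 102/125 has −14.0 (met).

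These counts were picked to show that disagreement is possible. They are not a forecast.

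**The case against.** The strongest reply is that the group is small and already visible. Entry requires a subject judged able and willing to take the preparation. Subjects are hospitalised and dosed on the day of randomisation, any partial intake puts them in ITT, and difficulty with drinking leads to a nasogastric tube. The 4% allowance covers all dropout and non-compliance, so giving all of it to pre-dose refusal in one arm is an extreme. An imbalance in non-starters would show in the SAP 3.2.4 tables, and a reader could count them as failures by hand. All of this stands, and it limits the size of the point. It does not supply the missing estimate.

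A second reply concerns the remedy. Redefining ITT as all randomised subjects would disturb other parts of the plan. PP takes its dose requirement from ITT, time to clear effluent runs from first intake, acceptability is rated per dose, and the 10% rule for repeating analyses compares other sets with ITT. This stands too, and the fix below avoids it.

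A reader might infer more than the documents support:

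- *That the plan conceals non-starters.* It does not; their numbers and reasons are tabulated by arm.
- *That the randomised comparison is lost.* ITT and mITT both analyse subjects as randomised. What is lost is only those who take nothing.
- *That the omission favours Eziclen.* The direction is unknown. Given the volumes and the protocol's remarks on PEG, refusal may be likelier on Klean-Prep, and leaving those subjects out would work against Eziclen.

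**Conclusion.** The gap is real and modest. No planned efficacy analysis includes subjects who decline the allocated preparation before any intake, although they know their arm, and the effect on the primary result is never estimated. The size is about 0.7 points per refuser, and at most about 3.4 points if five fall in one arm only. With equal refusal in both arms the difference does not move, and at five each the lower limit goes only from −9.0 to −9.6. These figures rest on 85% success among dosed subjects, complete assessment of those dosed, and an assumed range of 0 to 5 refusers per arm.

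This does not show that the sample size is wrong, that mITT should be replaced as the primary set, or that the non-inferiority conclusion would change. It supports one inexpensive addition.

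**What to change.** 1. Keep mITT as the primary set.
2. Keep the present dosed set for secondary and other endpoints and as the base for PP, but relabel it in SAP 2.1.1 and Protocol 10.1, for example as 'treated, as randomised', so that the name does not suggest all randomised subjects.
3. In SAP 3.2.1.1, add one sensitivity analysis of the primary endpoint on all randomised subjects by allocated arm. Count every never-dosed subject, and any other subject without a primary assessment, as a failure. Counting them regardless of the stated reason keeps the analysis on the randomised groups and avoids relying on reasons given by subjects who know their arm.
4. Read it beside the exclusion table already planned in SAP 3.2.4; no further tabulation is needed.

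The cost is a change of label wherever the set is named, one paragraph and one table. Allocation and the reason for not receiving treatment are already recorded, so no new data are needed. The drawback is a sensitivity estimate that may be slightly less favourable. If there are no never-dosed subjects, the analysis will show that this concern has no effect.

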2.1.1 Modified Intention-To-Treat population (mITT)

The mITT population is:

All randomised subjects who received even a partial dose of study treatment and produced a primary efficacy assessment.

Subjects will be assessed according to their randomised treatment, regardless of the treatment they receive.

